### 6.1.3 Height and weight

Height and weight will be measured, or taken from the most recent visit documentation if visit was within 1 week of enrollment.

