## 7.3 Statistical Methods

## 7.3.1 Baseline Data

The characteristics of the dose and placebo groups will be described using standard statistics (e.g. means, medians, standard deviations, or proportions). For all analyses, high dose group will continue to be evaluated together, despite slight change in concentration. Subgroup analysis will be done to evaluate any differences in those subjects who received the full 60 g/d dosing before this dose was decreased, versus the current 54 g/d dosing. Graphical procedures will be used to assess distributional assumptions and particularly the assumption of normality of outcome.

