## 7.3.2 Primary Efficacy Analysis

The primary intent to treat analysis will include all subjects who enroll and contribute at least 10 days of data to the study. The mean trajectory in decline and recovery in processing speed is unknown. Thus the primary analysis will aim to determine whether there are differences in processing speed between the BCAA dose groups and placebo, and if so, at what time periods the differences are most pronounced. The primary analysis will focus on results for the first 10 days of the study when we anticipate that the majority of subjects will be highly compliant. We will model processing speed as a function of dose and day of study and will allow differences between dose groups to vary as a function of time through a series of interaction terms. To ensure that the number of interaction terms does not become too large, we will consider groups of two to four time points, looking specifically at whether

04/06/2018 V 0.16

there are differences between any of the dose groups and placebo at Days 1-2, 3-6, 7-10, 11-14, 15-18, 19-21. The primary analysis will consider three key time periods, Days 3-6, 7-10 and 11-14 when we expect differences in processing speed between the BCAA-treated groups and placebo to be largest. Since processing speed differs with age, the model will be adjusted for age to account for any imbalances in age between dose groups. A mixed effects model will be used to account for correlations between repeated measurements on individual subjects. Likelihood ratio tests will be employed to specifically test whether there are differences in mean processing speed between placebo and any of the BCAA doses at the three key time periods. These three global tests will be conducted at a family-wise error rate of 0.05, using a Bonferroni correction to account for the three individual global tests. If statistical significance is achieved for the global test, we will then compare individual dose levels to placebo within time periods, again using a correction for four multiple tests per key time period.

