We note that with five treatment groups and 21 time points, there are a very large number of possible hypothesis tests that can be carried out with these data. If all of these tests were carried out without adjusting for multiple comparisons, we would undoubtedly find spurious associations. On the other hand, adjusting for large numbers of multiple comparisons substantially reduces the statistical power of a study. By focusing our testing for the primary efficacy analysis on three key periods where we adjust for a limited number of tests, we balance the need for a rigorous statistical testing procedure with a need to maintain statistical power.

An analysis of the Day 1-2, 15-18 and 19-21 data will follow the same format, but will be considered secondary and will not be formally corrected for multiple testing. In addition to hypothesis testing, we will estimate and plot means and confidence intervals for each group at each time point. This analysis will guide the recommendation for dose levels and evaluation times for the primary analysis in future efficacy studies.

With concerted efforts from our study coordinators and study staff we are hopeful that we can maintain excellent compliance throughout the study. In particular we expect good compliance early in the study when patients are highly motivated to feel better and return to school, work and play. However, we allow that some patients may have difficulty with compliance due to their injury, or become non-compliant once their symptoms improve. As part of this feasibility study, we will explore patterns of missing data, in particular how they may relate to the observed response (e.g. more missing data in those subjects who show better or worse processing speed) to compliance (e.g. more missing data in subjects who regularly fail to consume their supplements) and to demographics e.g. gender, age. This information will be valuable in planning future efficacy trials, and will guide our efforts to adjust for missing data. For example if the probability of missing data is associated with outcome, then non-ignorable missing data methods will be needed, whereas missing at random assumptions will be valid if the missing data can be explained by covariate information.

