#### 7.3.3 Analysis of Secondary Endpoints

Secondary endpoints, including clinical symptoms such as the posturography and sleep assessments, and the learning, attention and working memory components of the neurocognitive battery will be modeled using a similar approach as described above for the primary efficacy analysis (Section 7.3.2), with the goal of assessing differences between groups over time, after adjustment for age differences. We will assess the distribution of the outcome and either use a transformation to achieve approximate normality or use a generalized mixed effects model. Time to event outcomes (e.g. time to return to school or sports participation) will be modeled using a Cox proportional hazards model. We will secondarily adjust our primary models for body mass index (BMI) and compliance to obtain information on whether individuals with lower BMI, and presumably higher BCAA/kg dosing have better outcome.

We will also monitor compliance including adherence to treatment and daily completion of neurocognitive testing. It is of interest to determine whether there are differences in compliance among the dosage groups versus placebo whether compliance decreases as a function of time, and whether compliance differs among groups over time. Adherence to treatment is measured in terms of number of bottles of consumed per day (0, 1, or 2) and will be modeled as an ordinal outcome. Adherence to treatment will be assessed using generalized estimating equations (GEE) models as we have repeated measures on adherence for each subject across all time points in the study and are primarily interested in differences between groups. In particular we anticipate that with regular prompting and encouragement, subjects will consistently complete their neurocognitive functioning tests up until about 10 to 14 days into the study. We anticipate that compliance may begin to decrease around the 10 to 14 day point as subjects begin to feel better and return to their normal routines. Assessment of compliance will be key information needed to design the anticipated pivotal trial of subsequent research studies.

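### A single BMI term cannot show a dose-per-kilogram effect, and compliance should not be a covariate in the same secondary model

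*Combined protocol and SAP*

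**What the plan says.** The secondary model and its purpose are given in one sentence of section 7.3.3: "We will secondarily adjust our primary models for body mass index (BMI) and compliance", in order to find out "whether individuals with lower BMI, and presumably higher BCAA/kg dosing have better outcome".

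The primary model is set out in section 7.3.2. It contains dose, day of study grouped into periods, and age, and it "will allow differences between dose groups to vary as a function of time through a series of interaction terms". No other interaction is named. Its tests ask about differences "test whether there are differences in mean processing speed between placebo and any of the BCAA doses at the three key time periods" (section 7.3.2 continues the sentence that begins with the likelihood ratio tests), so placebo is in the model. No BMI-by-dose term, no g/kg variable and no restriction to the active arms appears anywhere.

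Doses are fixed in grams per day (section 8.1.3). Body size is recorded at entry: "Height and weight will be measured, or taken from the most recent visit documentation" (section 6.1.3). The two top-dose concentrations used during the trial are combined: "high dose group will continue to be evaluated together, despite slight change in concentration" (section 7.3.1).

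On compliance, section 7.3.2 allows that "some patients may have difficulty with compliance due to their injury, or become non-compliant once their symptoms improve". Section 7.3.3 treats it as an open question "whether compliance differs among groups over time". It does not say which measure of compliance (bottles taken, urine deuterium or completed tests) enters the adjusted model.

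**The concern.** There are two separate faults in one model.

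- **BMI.** A placebo subject receives 0 g/kg at every BMI, and the g/kg gradient with body size differs across the four active arms. One BMI slope over all five arms mixes those gradients with any relation between BMI and reaction time that has nothing to do with treatment. BMI is also not the denominator of interest. Weight is, and weight is recorded.
- **Compliance.** It is observed after randomisation, the plan itself links it to recovery, and it may differ by arm. Conditioning on such a variable breaks the randomised comparison and can bias the dose-placebo contrasts in this model in either direction.

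What is at stake is interpretation. A BMI association could be reported as evidence on dose per kilogram and carried into later trials, and the adjusted contrasts could contradict the randomised ones for reasons unrelated to treatment.

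**Working it through.** **Inputs from the plan (section 7.4):** 10 subjects per group, three measurements per period, SD 0.10 s, intra-class correlation 0.5, two-sided 0.05 divided by four contrasts.

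**The plan's own figure.** SD of a three-day mean = 0.10 × √((1 + 2 × 0.5)/3) = 0.0816 s. Detectable difference = (2.498 + 0.842) × 0.0816 × √(2/10) = 0.122 s at 80% power. This reproduces the plan. No figure is given for the BMI and compliance model.

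**BMI as a proxy for weight.** The heights are assumed. At BMI 22:

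- 1.45 m: weight 22 × 1.45² = 46.3 kg; 54/46.3 = 1.17 g/kg/d.
- 1.90 m: weight 22 × 1.90² = 79.4 kg; 54/79.4 = 0.68 g/kg/d.

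The ratio is 1.7 at identical BMI.

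**The planned BMI term.** The documents give no BMI distribution and no BMI effect, so these are assumptions: BMI SD 3.2, age uniform on 11 to 34, weight at least 40 kg. Model: dose group + age + BMI, 50 subjects, residual SD 0.0816, 4,000 simulated trials. As a rough check, the standard error of the slope is 0.0816/(3.2 × √43) = 0.0039 s per unit.

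| True situation | BMI effect (s per unit) | BMI term p < 0.05 |
|---|---|---|
| No drug effect | 0 | 5% |
| No drug effect | 0.005 | 24% |
| No drug effect | 0.0075 | 44% |
| No drug effect | 0.010 | 68% |
| Per-kg effect only | 0 | 11% |

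The per-kg effect in the last row is 0.122 s at 54 g/d for a 65 kg subject: 54/65 = 0.831 g/kg/d and 0.122/0.831 = 0.147 s per g/kg/d.

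A second simulation with BMI SD 4, mean height 1.68 m and height SD 0.09 m gave 5%, 35%, 84% and 99% for BMI effects of 0, 0.02, 0.04 and 0.06 s per SD (0, 0.005, 0.010 and 0.015 s per unit). The rates move with the assumptions; the confounding does not.

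**The alternative.** Model: dose group + weight + age + sex + g/kg/day.

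- The g/kg term is significant in 5% of trials when the true effect depends on grams only, and in 5% with no drug effect and a BMI effect of 0.0075 s per unit.
- Its power against 0.147 s per g/kg/d is 12% with all top-arm subjects at 54 g/d and 14% with half at 60 g/d. The mean 95% half-width is about 0.35 to 0.38 s per g/kg/d.
- Dose group must stay. Without it, g/kg is significant in 94% of trials when the true effect depends on grams only.
- A dose-by-weight interaction behaves similarly: 4% to 5% false positives, 11% to 12% power.

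**Compliance.** Assumptions: compliance changes by 0.2 bottles/day per 0.1 s of a subject's underlying level (2 bottles/day per s), noise SD is 0.25 bottles/day, and the active arm takes 0.2 or 0.4 bottles/day fewer. Between-subject variance = 0.5 × 0.10² = 0.005. The within-arm slope of outcome on compliance is (2 × 0.005)/(4 × 0.005 + 0.25²) = 0.01/0.0825 = 0.121 s per bottle/day. Bias under no drug effect = 0.121 × gap: 0.024 s at 0.2 and 0.048 s at 0.4. Simulation of 20,000 two-arm trials agrees (positive means the active arm looks slower):

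| True effect | Arm gap | Better subjects comply less | Worse subjects comply less |
|---|---|---|---|
| 0 | 0 | 0.000 | 0.000 |
| 0 | 0.2 | +0.024 | −0.024 |
| 0 | 0.4 | +0.048 | −0.049 |
| −0.122 | 0 | −0.093 | −0.094 |
| −0.122 | 0.2 | −0.068 | −0.117 |
| −0.122 | 0.4 | −0.043 | −0.141 |

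Without the adjustment, the null contrast is 0.000 throughout. With a true effect, the adjusted estimate is biased even when the arms have no built-in gap, because a treatment that speeds recovery also changes compliance.

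**The case against.** The plan says only that it will adjust. It never writes that BMI enters as a single slope pooled over placebo, and it sets no test or significance rule for BMI. That is true. The single slope is an inference, but it is what the wording describes when the only interactions named are dose by time. If an interaction was intended, the text needs the same edit. The rejection rates therefore show how easily the term could mislead, not the error rate of a stated test.

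Every effect size is assumed. Nothing in the documents says BMI predicts processing speed, and with no such effect the rate is the nominal 5%. That stands against the magnitudes but not the logic: the term cannot tell the two explanations apart. The 1.7-fold height example is also an extreme one, and the age term would absorb part of it in the youngest subjects.

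On compliance, the plan expects good adherence early, with a decline around days 10 to 14. Two of the three key periods largely precede that, and under no drug effect there is no bias unless the arms differ. This limits the likely size, but Days 11-14 remain exposed and the plan itself leaves the arm difference open.

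Finally, the replacement has about 12% to 14% power against 11% for the planned term. The gain is validity, not precision: its false-positive rate stays near 5% where the BMI term's does not.

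**Conclusion.** The concern holds. As worded, the model cannot support the per-kilogram reading the plan gives it, and compliance is an unsuitable covariate there. With no drug effect, the BMI term is significant in 24% to 68% of simulated trials for assumed BMI effects of 0.005 to 0.010 s per unit, yet it finds a true per-kilogram effect in only 11%. Compliance adjustment can move a null contrast by 0.024 to 0.049 s either way under the assumed links. These sizes rest on assumed body sizes, BMI effects and compliance patterns; the confounding itself does not.

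The reach is limited. This is a secondary model in an exploratory trial. The primary test, the sample size, and the group means and intervals that section 7.3.2 uses to recommend dose levels do not change.

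**What to change.** Rewrite the BMI and compliance sentence in section 7.3.3 as follows.

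- Keep randomised dose group and its time-period terms in the model.
- Replace BMI with baseline weight plus a g/kg/day term, or with a dose-by-weight interaction, adjusted for age and sex. The g/kg value is the subject's assigned g/d divided by recorded weight, and 0 for placebo.
- Because section 7.3.1 pools the 60 and 54 g/d subjects, compute g/kg from each subject's own assigned g/d, not from the group label.
- Remove compliance from this model. Keep the planned GEE analysis of adherence by arm, and label any analysis relating adherence to outcome as exploratory, stating which compliance measure it uses.
- Report the g/kg estimate with its 95% interval as descriptive. A half-width of about 0.35 to 0.38 s per g/kg/d against an assumed slope of 0.147 means it will rarely be conclusive.

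The cost is SAP wording only. Weight, assigned dose and adherence are already recorded, and neither the primary test nor the sample size changes.

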## 3.2 Secondary Objectives

The secondary objectives are to:

- Determine whether administration of BCAA's improves neurocognitive recovery compared to placebo for the cognitive domains of attention, learning, and working memory, and if so determine whether the results reflect differences in maximum levels of impairment or increases in subsequent speed of improvement.
- Evaluate whether BCAA supplementation improves clinical symptom resolution.
- Determine whether BCAA supplementation reduces the time to return to normal activities, specifically school or work, and participation in sports.
- Assess dose-related compliance of subjects with daily self-administration of BCAA's and with completion of study endpoints.
- Assess feasibility of enrolling potential subjects within 72 hours of concussion injury.
- Assess safety of BCAA supplementation in concussed patients.

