## 4.2 Allocation to Treatment Groups and Blinding

The study biostatistician, [name], will generate a randomization schedule for implementation in the randomization module of the study database system. The randomization scheme will be based on an equal allocation of each of the possible doses or placebo, and stratified based on sex. The randomization schedule is uploaded into the data management system (DMS) and provided to the Investigational Drug Service (IDS). The IDS will use the randomization schedule to prepare kits of BCAA doses or placebo for distribution. Upon confirmation of eligibility, the DMS will provide study personnel with a number that is then given to the IDS and corresponds to the kit number to be distributed. All study team members will be blinded to treatment assignment. The Database Administrator will have access to the link between the kit number and the treatment arm and will provide this information to the Investigational Drug Service (IDS) so that kits are prepared according to this scheme. BCAA and placebo treatment kits will appear identical.

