# 4.3.2 Total Number of Study Sites/Total Number of Subjects Projected

The study will be conducted through the Children's Hospital of Philadelphia and the Hospital of the University of Pennsylvania. Recruitment will stop when 50 subjects who are evaluable for efficacy are enrolled. A subject who is evaluable for efficacy is one who completes the study up until at least day 10 of the study. It is expected that approximately 72 subjects will be enrolled to produce 50 such subjects. All subjects who enroll and receive study medication will be evaluable for safety.

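### Adherence GEE with 10 to 14 subjects per arm names no small-sample method; under usual practice, tests of dose differences reject too often, modestly for single contrasts and more for joint tests

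*Combined protocol and SAP*

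**What the plan says.** All references are to the combined protocol and SAP.

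- Section 3.2 lists as a secondary objective: "Assess dose-related compliance of subjects with daily self-administration of BCAA's".
- Section 7.3.3 defines adherence as the "number of bottles of consumed per day (0, 1, or 2) and will be modeled as an ordinal outcome". The method is given in one clause: "Adherence to treatment will be assessed using generalized estimating equations (GEE) models". The reasons offered are the repeated measures on each subject and a main interest in group differences.
- The same section poses three questions: dose groups against placebo, change over time, and "whether compliance differs among groups over time".
- Section 7.3.2 describes the design as having "five treatment groups and 21 time points". Section 4.2 states: "The randomization scheme will be based on an equal allocation of each of the possible doses or placebo", with stratification by sex. Section 4.3.2 expects that "approximately 72 subjects will be enrolled to produce 50 such subjects".
- Section 7.3.3 does not state a working correlation, a variance estimator, a reference distribution, the form of the time terms, the analysis set, or a significance level for adherence.

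**The concern.** The robust (sandwich) variance normally used with GEE is justified when there are many independent subjects. Twenty-one daily reports per subject do not make up for having few subjects. With 10 to 14 per arm, the fitted model absorbs part of each subject's deviation, so the estimated variance tends to be too small. The problem grows when most subjects take nearly every bottle, because a few poor adherers then carry most of the between-subject variance.

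At stake is whether an apparent dose difference in adherence can be trusted. Section 7.3.3 describes compliance as key information for designing the later pivotal trial, and Section 7.3.2 itself warns about spurious associations from testing without control. A test that is nominally 5% but rejects more often could feed a false dose signal into that planning.

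**Working it through.** **The plan's own figure.** None is given for adherence. The only computable design figure is the 0.122 second detectable difference in Section 7.4, and it reproduces. Effective SD = 0.10 × √((1 + 2 × 0.5)/3) = 0.0816. Detectable difference at two-sided 0.05/4 = 0.0816 × √(2/10) × (2.498 + 0.842) = 0.122. This confirms 10 per arm as the evaluable basis.

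**Arm sizes.** 50/5 = 10 evaluable and 72/5 = 14.4 enrolled. Section 7.3.3 does not say which set applies to adherence, so both were run.

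**Assumed, because the documents are silent.**
- Share of two-bottle days: 52% to 83%, with a decline after day 10.
- Subject random intercept on the cumulative-logit scale: SD σ = 1.5 or 2.5. Latent ICC = σ²/(σ² + π²/3), so 2.25/(2.25 + 3.29) = 0.41 and 6.25/(6.25 + 3.29) = 0.66.
- Missingness: none, or 30% dropout plus 10% sporadic.

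**Analysis simulated.** Cumulative-logit GEE with independence working correlation, subject as cluster, uncorrected sandwich, five arms, 21 days and no true dose difference. A single contrast rejects if |b|/SE > 1.96. The joint test refers b′V⁻¹b for the four dose terms to chi-square on 4 df. There were 1,500 replicates per setting.

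Each cell shows no missing data / with missing data.

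| Per arm | Two-bottle days | Latent ICC | Robust SE ÷ true SD | Single contrast, % | Joint 4-df, % |
|---|---|---|---|---|---|
| 10 | 52% | 0.41 | 0.96 / 0.94 | 6.8 / 7.8 | 12.3 / 14.3 |
| 10 | 67% | 0.66 | 0.91 / 0.89 | 8.4 / 9.3 | 14.9 / 18.3 |
| 10 | 73% | 0.41 | 0.91 / 0.89 | 9.2 / 10.1 | 15.3 / 18.1 |
| 10 | 83% | 0.66 | 0.82 / 0.81 | 12.3 / 13.1 | 25.1 / 26.9 |
| 14 | 52% | 0.41 | 0.96 / 0.97 | 6.4 / 6.3 | 9.4 / 10.1 |
| 14 | 68% | 0.66 | 0.93 / 0.94 | 7.2 / 7.0 | 11.4 / 11.9 |
| 14 | 73% | 0.41 | 0.94 / 0.92 | 7.6 / 8.2 | 13.3 / 14.2 |
| 14 | 83% | 0.66 | 0.89 / 0.85 | 9.8 / 10.6 | 18.1 / 20.2 |

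Monte Carlo error is about 1 point: √(0.27 × 0.73/1500) = 0.011 at the top of the joint range. Shorter 600-replicate runs agree within simulation error, peaking at 15% (single) and 30% (joint).

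**Consistency check.** If the SE is r times the true SD, a 1.96 cut-off rejects 2Φ(−1.96r): about 6% at r = 0.97 and about 11% at r = 0.81. Instability of the SE itself adds the rest of the single-contrast excess. The joint test is worse because it inverts a poorly estimated 4 × 4 covariance matrix.

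**Group by time.** With a linear day term (4 df), rejection is 9.5% to 31%. With the six periods of Section 7.3.2 (4 × 5 = 20 df), if those were used here, it is 47% to 98%, with frequent non-convergence.

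**Bias-corrected variance (Mancl-DeRouen, t/F reference on N − 5 df).**
- At 52% to 73% two-bottle days: single contrast 3.8% to 6.8%, joint test 3.8% to 9.8%.
- At 83%: single contrast 7.6% to 10%, joint test 15% to 19%.

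**Permutation of subject mean bottles per day.** Four settings with 600 replicates gave 5.5%, 5.7%, 7.5% and 5.5%. The 7.5% is 45 rejections against 30 expected, about 2.8 Monte Carlo SEs high, so the unstratified test was re-run with 4,000 replicates per setting. That gave 5.2%, 5.2%, 4.3% and 5.6%, so the high reading did not recur.

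**Separate check.** A binary GEE for full adherence with uncorrected sandwich gave 6.5% to 9% (single) and 9% to 17% (joint), against about 4% to 6% for permutation.

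**The case against.** The strongest reply is that the plan names only GEE and an ordinal outcome. It specifies neither a Wald test nor an uncorrected sandwich, so a corrected or permutation analysis would comply with it as written. Adherence is a secondary, feasibility-type question with no alpha and no decision rule. It is also checked by urine deuterium and returned bottles (Section 8.1.4). Nothing restricts the analysis to the evaluable set, so 14 per arm may be the more natural case, and the 27% figure belongs to 10 per arm. High adherence is not assured either: Section 7.3.2 is hopeful, but Section 5.2 reports early compliance problems.

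Most of this stands and limits the claim. The gap is an omission rather than a stated wrong choice, and the upper ends of the ranges need very high adherence. But conventional software output would fill the omission with the uncorrected variance. Even at 14 per arm and moderate adherence, the joint test rejects 9% to 14%. An exploratory label does not make a mis-sized p-value more informative.

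A reader might infer that the robust standard errors are far too small and that any dose difference would be declared at several times the nominal rate. The figures do not support this. The shortfall is 3% to 19%, single contrasts reject at 1.3 to 2.6 times nominal, and only multi-df tests, whose form the plan does not fix, reach severalfold. A reader might also infer that a dose would be labelled poorly tolerated on this model. Section 7.2 bases tolerability on adverse events and lists compliance separately.

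**Conclusion.** The concern holds as an omission with a measurable consequence. With the usual uncorrected sandwich, a nominal 5% single dose-placebo contrast rejects about 6% to 13%. A joint 4-df dose test rejects about 9% to 27%, roughly 2 to 5 times nominal, and group-by-time tests are also inflated. Direction and rough size agree across separate simulations. The exact figures rest on assumed adherence, between-subject variation and missingness, and on an independence working correlation. A variance correction alone is not enough at very high adherence, whereas permutation held its level in the settings tested. This is worth settling before the adherence data are analysed, but it does not touch the primary analysis.

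**What to change.** Add a short inference rule to Section 7.3.3:

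- Keep ordinal GEE for estimates and the time profile. State the working correlation and a limited set of time terms.
- Take dose p-values from a permutation test of subject-level mean bottles per day, permuting arms within sex strata to match the randomisation.
- For group-by-time, apply the same permutation to a subject-level change, for example early mean minus late mean.
- State the analysis set, and how unreported days and days after withdrawal enter the subject means, since dropout may differ between arms.
- Report GEE intervals with bias-corrected (Mancl-DeRouen) standard errors and t quantiles. Label them descriptive, and note that they may remain somewhat too narrow at very high adherence and may not always agree with the permutation p-value.

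The cost is a few sentences, minor programming and wider intervals. The subject mean treats 0, 1 and 2 bottles as equally spaced, and an early-late change gives less detail than a full profile. Conduct, data collection and sample size are unaffected.
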